### Boehringer Ingelheim BI Trial No.: 1366-0055 c42374778-02 Clinical Trial Protocol

Page 97 of 98

Proprietary confidential information © 2023 Boehringer Ingelheim International GmbH or one or more of its affiliated companies

	events (please see section 5.2.6.2.1 ), or last contact date in case		
	of lost to follow-up."		
Rationale for change	deletion as it is no applicable for our study		
Section to be changed	3.3.4.1 Discontinuation of trial treatment		
Description of change	Text added :		
	• the trial participant develops an AE:		
	• CTCAE Grade 3 or higher and the AE was		
	assessed by the Investigator as related to the		
	trial treatment; OR		
	• CICAE grade 4 or higher regardless of		
	attribution to the trial treatment		
Rationale for change	Request from Health Authority		
Section to be changed	3.3.4.1 Discontinuation of trial treatment		
Description of change	Text added :		
	Boehringer Ingelheim will closely monitor and medically		
	review all adverse events CTCAE Grade 3 and higher.		
	BI will pause the enrollment of new patient in the trial and		
	ensure the clinical data is reviewed by the data monitoring		
	committee (DMC) for safety before proceeding with the trial if		
	one of the following occurs:		
	1. more than two patients develop a CTCAE grade 3 or		
	higher in the same category;		
	OR		
	2. two or more patients meet the individual patient		
	stopping criteria related to adverse event		
Rationale for change	Request from Health Authority		
Section to be changed	5.2.3 Safety laboratory parameters /		
Description of change	1 ext added in Table 5.2.3: 1 Safety laboratory tests:		
	- Haematology: Haemoglobin		
	- RBC count / erythrocytes		
	- Automatic WBC differential (absolute and percentage)		
	- Brain Natriuretic Peptide (BNP)		
Rationale for change	Correction as these parameters were mentioned in different		
	section of the protocol but not listed in the table		
Section to be changed	Table 5.2.3: 1 Safety laboratory tests		
Description of change	Correction of the Superscript number of the following		
	parameters:		
	Alpha fetoprotein + correct to Alpha fetoprotein4		
	$CK-MB^{\pm}$ corrected to $CK-MB^{1}$		
	Phosphatidylethanol (PEth)  corrected to Phosphatidylethanol		
	(PEth) 		
	Troponin I <math>\pm</math> corrected to Troponin I 		

### Boehringer Ingelheim BI Trial No.: 1366-0055 c42374778-02 Clinical Trial Protocol

Page 98 of 98

Proprietary confidential information © 2023 Boehringer Ingelheim International GmbH or one or more of its affiliated companies

	Infections screening6 corrected to Infections screening 		
Rationale for change	Correction		
Rationale for change			
Section to be changed	Table 5.2.3: T Safety laboratory tests		
Description of change	The text in bold has been added to footnote#2 and deleted in		
	footnote #3		
	i.) Footnote #2 : Not performed at screening (Visit 1a). PEth, an		
	alcohol-specific biomarker, will be measured during the		
	treatment period for data analysis purposes		
	ii.) Footnote#3 : Not performed at screening (Visit 1a) or EoS; collect		
	seated after patient seated for at least 5 to 15 minutes, and once		
	patient has been out of bed for at least 2 hours		
Rationale for change	i. Clarification for the purpose of the assessment of PEth		
8	ii. Correction as it not applicable for the safety parameters		
	linked to superscript 3		
Section to be changed	7.2.1 General considerations		
Description of change	Deletion of bold text :		
	this analysis set includes all enrolled trial participants that were		
	entered or randomised		
Rationale for change	Administrative correction		

2. LIST OF ABBREVIATIONS

Term	Definition / description
ALQ	Above Limit of Quantification
ALT	Alanine transaminase
ANCOVA	Analysis of Covariance
AST	Aspartate transaminase
BLQ	Below Limit of Quantification
BMI	Body mass index
DBP	Diastolic blood pressure
FHVP	Free hepatic venous pressure
Fib-4	Fibrosis-4
HVPG	Hepatic Venous Pressure Gradient
LLOQ	Lower limit of quantification
PFHVP	Proximal free hepatic venous pressure
RS	Randomised Set
SBP	Systolic blood pressure
SD	Standard deviation
TS	Treated Set
ULN	Upper Limit of Normal
ULOQ	Upper limit of quantification
WHVP	Wedged Hepatic Venous Pressure

1366-0055

c43185880-01

Proprietary confidential information © 2024 Boehringer Ingelheim International GmbH or one or more of its affiliated companies.

3. INTRODUCTION

As per ICH E9 (9.1), the purpose of this document is to provide a more technical and detailed elaboration of the principal features of the analysis described in the protocol, and to include detailed procedures for executing the statistical analysis of the primary and secondary variables and other data.

This TSAP assumes familiarity with the Clinical Trial Protocol (CTP), including Protocol Amendments. In particular, the TSAP is based on the planned analysis specification as written in CTP Section 7 "Statistical Methods and Determination of Sample Size". Therefore, TSAP readers may consult the CTP for more background information on the study, e.g., on study objectives, study design and population, treatments, definition of measurements and variables, planning of sample size, randomization.

The statistical analyses will be performed within the validated working environment CARE, including SASTM (current Version 9.4, by , and a number of SASTM-based tools (e.g., macros for the analyses of AE data or laboratory data; Report Appendix Generator system (RAGe) for compilation/formatting of the Clinical Trial Report (CTR) appendices). Pharmacokinetic (PK) parameters will be calculated using WinNonlinTM software (version 8.1,

Proprietary confidential information © 2024 Boehringer Ingelheim International GmbH or one or more of its affiliated companies.

4. CHANGES IN THE PLANNED ANALYSIS OF THE STUDY

The Avenciguat program in patients with clinically significant portal hypertension (CSPH) is decided to be discontinued in May 2024. No subject has finished the 8-week treatment duration, leading to no HVPG data at Week 8 collected. Therefore, planned analysis around HVPG data in the CTP, i.e.,

- percentage change in HVPG from baseline after 8 weeks of treatment,
- occurrence of a response, which is defined as > 10% reduction from baseline HVPG after 8 weeks of treatment,

will not be performed. Only listing will be prepared.

Consequently, the reporting of intercurrent event, which supports HVPG analysis, is no longer of interest. All subjects are decided to be early discontinued.

c43185880-01

Proprietary confidential information © 2024 Boehringer Ingelheim International GmbH or one or more of its affiliated companies.

5. ENDPOINTS(S)

5.1 PRIMARY ENDPOINT(S)

The primary endpoint is defined as the percentage change from baseline in HVPG (measured in mmHg) after 8 weeks of treatment.

The average wedged hepatic venous pressure (WHVP) and the average free hepatic venous pressure FHVP (FHVP) will be calculated based on the triplicate measurements.

Either the average FVPG or the measured proximal free hepatic venous pressure (PFHVP) will be used as the subtrahend for the calculation of HVPG (rounded to one decimal place).

Based on the judgment of the central reader, if the recorded PFHVP is considered to be more reliable than the recorded FHVP, then:

HVPG (mmHg)=average WHVP (mmHg) – PFHVP (mmHg);

if the recorded FHVP is considered to be more reliable than the recorded PFHVP, then

HVPG (mmHg)=average WHVP (mmHg) – average FHVP (mmHg).

5.2 SECONDARY ENDPOINT(S)

5.2.1 Key secondary endpoint(s)

Since there are no key secondary endpoints specified in the CTP, this section is not applicable.

5.2.2 Secondary endpoint(s)

The secondary endpoints will be used as defined in CTP Section 2.1.3.

c43185880-01

c43185880-01

c43185880-01

Proprietary confidential information © 2024 Boehringer Ingelheim International GmbH or one or more of its affiliated companies.

6 GENERAL ANALYSIS DEFINITIONS

6.1 TREATMENT(S)

For basic study information on the treatment to be administered, assignment to treatment, and selection of dose, refer to CTP Section 4.

There will be three treatment study phases in this trial: screening, double-blind study treatment phase (with Avenciguat and matching placebo) and follow-up.

Label	Interval	Start date	End date		
Screening	Screening	Date of informed consent	Date of first administration of double-blind study medication - 1		
Placebo/ Avenciguat 3mg	On-treatment Date of first administration of double-blind study medication		Date of last intake of study medication + X		
Follow-up	Follow-up	Date of last intake of study medication + X + 1	Latest of (date of EOS visit, last contact date on EOS page)		

Table 6.1: 1Flow chart of analysis phase

* X=3 or REP (7 days) for safety laboratory and AE respectively; X for other variables are defined in Table 6.7:
 1. Follow-up phase might not exist, e.g., if the patient's trial termination date is within 7 days after last administration of study drug.

The purpose of the definitions above is to describe all the different study/treatment intervals, to which a patient can be assigned during the course of the trial. Note that the term "treatment regimen" can also cover time periods with no active treatment.

For efficacy analyses of HVPG, data up to REP+1 (8 days) after last treatment intake will be considered as on-treatment, because a HVPG measurement at EOT is allowed to be done within 7 days after scheduled EOT (i.e, REP+1 days after last dose) as Section 5.1.1 of the CTP states "HVPG measurements should be performed on the day of the scheduled visit, or within seven days (if this latter approach is taken, the measurement should still be performed after an overnight fast / after a fast of at least four hours)

The efficacy analyses will follow the intention-to-treat (ITT) principle in assigning patients to treatment groups, i.e. patients will be analyzed in the treatment group they were randomized to.

In addition, AEs with an onset during the time of the incorrect study treatment will be listed separately.

66-0055 c43185880-01 Proprietary confidential information © 2024 Boehringer Ingelheim International GmbH or one or more of its affiliated companies.

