#### Residual Effect Period

The Residual Effect Period (REP) of BI 685509 is 7 days. This is the period after the last dose with measurable drug levels and / or pharmacodynamic (PD) effects still likely to be present.

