### 6.2.2.1 End of treatment / Early discontinuation visit

Patients who successfully complete the entire 8 week treatment period should have the assessments for the EoT visit performed as indicated in the Flow Chart. Such patients should be registered as completed in the IRT system. End of trial medication must also be recorded on the corresponding eCRF.

For patients who discontinue trial medication prematurely (for whatever reason), an ED visit (refer to the Flow Chart) should be completed instead of the planned treatment period visit (refer to Section 3.3.4.1). Ideally the ED visit should be performed within seven days of discontinuing the trial medication. The assessments performed at the ED visit should be in accordance with the Flow Chart, with the following exceptions:

- HVPG: not required
- •
- •
- biobanking sampling: not required

Patients who discontinue treatment early should be registered as discontinued in the IRT system. End of trial medication must also be recorded on the corresponding eCRF.

At the EoT and / or ED visit, patients should be reminded about restrictions (refer to Section 4.2.2) that still need to be observed up until the EoS visit (refer to Section 6.2.3). Home BP and HR monitoring should continue between the EoT / ED visit and the EoS visit.

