6.7 BASELINE, TIME WINDOWS AND CALCULATED VISITS

Regarding efficacy and safety endpoints, the term "baseline" refers to the last observed measurement prior to administration of any study medication.

Measurements taken prior to the first intake of study medication will be considered pretreatment values. Pre-treatment values will be assigned to a visit according to the nominal visit number as recorded on the eCRF or as provided by the laboratory.

In general, the date of the first drug administration will be used to separate pre-treatment from on-treatment values. Measurements taken after first trial medication intake will be considered on-treatment values if they have been obtained up to end of the parameter specific follow-up period as defined in Table 6.7:1 below and will be assigned to the corresponding study medication for efficacy and safety analyses.

c43185880-01

Proprietary confidential information © 2024 Boehringer Ingelheim International GmbH or one or more of its affiliated companies.

Measurements taken after the end of the endpoint specific follow-up period will be considered post-treatment values.

Endpoint	Last day of assignment to treatment phase (days after study medication stop date)
Efficacy	
HVPG	8 (REP + 1)
Fibroscan data	8
Biomarkers	1
Safety	
Adverse events	7
Safety laboratory measurements	3
Vital signs (including body weight, blood pressure)	1

 Table 6.7: 1
 Parameter specific follow-up period for the assignment to treatment phase

For derivation of the last value on treatment, minimum value on treatment, and maximum value on treatment, all values from the relevant phase (whether or not collected in any time window; see Table 6.1:1 for definition of the trial phases) will be considered; these will be derived for analysis of laboratory and vital signs data. For identification of potentially clinically significant abnormal laboratory values, all values (whether selected in any time window) up to 7 days after last treatment intake will be considered.

On-treatment efficacy, safety and biomarker measurements will be assigned to visits based on the extended time windows around the planned visit dates, defined relative to the day of first trial medication intake (see Table 6.7:2).

c43185880-01

Proprietary confidential information © 2024 Boehringer Ingelheim International GmbH or one or more of its affiliated companies.

Visit		Dlannad	Time window (Days)				
number	Visit label	day	Window	Start	End	Start	End

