/name	v isit idoci	uay	(per CTP)	(per CTP)	(per CTP)	(extended)*	(extended)*
V1	Screening	-28				-∞-	0
			On-ti	reatment			
V2	Week 0	Day 1	N/A	1	1	≤ 1	1
V3	Week 1	Day 8	+2	8	10	2	11
V4	Week 2	Day 15	[contact]
V5	Week 4	Day 29	[contact]
V6	Week 6	Day 43	± 3	40	46	37	50
V7	Week 8/ EoT	Day 57	±5	52	62	51	Study medication stop date + X [#] days
			Off-t	reatment			
V8	Week 10/ EoS	Day 71	±5	66	76	Study medication stop date + X [#] days +1	Day of last follow-up value

T 11 (7)	TT' ' 1	c ·		• •.	C 1	1 *
I able 6 $/ \cdot /$	I ime windows	for assign	ment of measure	ments to visits	for statistical	analysis
1 4010 0.7.2		ioi ussign	ment of measure		101 Statistical	unuryono

Days are counted relative to the day of first treatment, which is defined as Day 1.

* Start (extended): End of extended window of last visit+1

End (extended): Midpoint of planned days between current visit and next visit

X= 3 days for safety laboratory; X=1 day for biomarkers and vital sign, respectively; X= 8 days (REP +1) for HVPG and fibroscan data.

The midpoint between two on-treatment visits defines the end of a time window, with the midpoint being included in the time window of the preceding visit. The end of the time window of the last on-treatment visit (end of treatment (EoT)) is endpoint dependent (Table 6.7:1).

Repeated and unscheduled efficacy and safety measurements will be assigned to the nominal visits and listed in the subject data listing according to the time windows described above. Only one observation per time window will be selected for analysis at an on-treatment visit - the value which is closest to the protocol planned visit day will be selected. If there are two observations which have the same difference in days to the planned day, the first value will be selected. If there are two observations on the same day, the first value will be selected. If there are multiple values within the time window of the last visit, including a value on the last day of drug intake, the value on the last day of drug intake is used as the value of the last visit.

Data prior to Day 1 of trial medication will be based on nominal visits and time windowing will not be applied. For these time points, data from the scheduled visit will always be selected if they are collected correctly. Unscheduled visits will only be considered if no correct data from the scheduled visit is available. If no correct data from a scheduled visit is

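### Early-discontinuation labs taken 4 to 7 days after the last dose fall within the 7-day residual effect period but are left out of the last-value, minimum/maximum, reference-range and eDISH displays

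*SAP*

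**What the plan says.** **When a lab counts as on-treatment.** The footnote to SAP Table 6.1:1 gives "X=3 or REP (7 days) for safety laboratory and AE respectively", counted in days after the last intake. Tables 6.7:1 and 6.7:2 repeat the 3 days for labs. For anything later, SAP 6.7 states: "Measurements taken after the end of the endpoint specific follow-up period will be considered post-treatment values".

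**The exception.** For potentially clinically significant lab abnormalities, SAP 6.7 says "all values (whether selected in any time window) up to 7 days after last treatment intake will be considered".

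**The residual effect period.** Protocol 1.2.1 states: "The Residual Effect Period (REP) of BI 685509 is 7 days". It explains: "This is the period after the last dose with measurable drug levels and / or pharmacodynamic (PD) effects still likely to be present".

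**The last treatment-phase visit.** SAP 4 reports that no participant finished 8 weeks and adds: "All subjects are decided to be early discontinued". For anyone who stops early, the protocol replaces the planned visit with an ED visit. Section 6.2.2.1 says: "Ideally the ED visit should be performed within seven days of discontinuing the trial medication". Footnote 3 of the flow chart gives the same 7 days.

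**Displays that use the on-treatment phase.** SAP 6.7 takes last, minimum and maximum on-treatment values from the phases of Table 6.1:1. SAP 7.8.2 builds the reference-range tables and the change from baseline on the last on-treatment value, and it restricts the eDISH plots to the on-treatment period.

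**The concern.** A 3-day window suits a participant who completes treatment, because the end-of-treatment visit is the morning after the last dose. In this trial nobody completes. The SAP is dated 1 July 2024, after the May 2024 decision to stop the programme. It drops the HVPG analyses for that reason but does not consider what the stop means for the lab window.

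The same sample can therefore be treated in two ways. An ALT value taken 5 days after the last dose counts in the abnormality table but not in the eDISH plot. If the investigator reports it as an adverse event, the event is on-treatment (7 days) while the lab value behind it is not (3 days). Hepatic injury is the trial's adverse event of special interest, so the end-of-exposure ALT, AST and bilirubin are values a reader will look for. With about 40 participants planned and an early stop, each one matters to these displays.

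**Working it through.** **1. The one window the SAP derives from a visit allowance.** For HVPG, the last dose is the evening before the end-of-treatment visit (1 day) and the measurement may follow within 7 days of that visit: 1 + 7 = 8 days. This matches the 8 days in SAP 6.1. HVPG will now only be listed. The same check was not made for labs, which will be analysed.

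**2. The same check for labs.** A value is post-treatment if its day after the last dose exceeds X.

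- Planned end-of-treatment visit: day 1 ≤ 3, so the lab is on-treatment. The mismatch concerns ED visits only.
- ED visit with X = 3: days 0 to 3 are on-treatment; days 4, 5, 6 and 7 are post-treatment.
- Share of permitted days outside the window: 4/7 = 57% for days 1 to 7, or 4/8 = 50% if day 0 counts.
- ED visit with X = 7: none of days 0 to 7 is outside.

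**3. What replaces the excluded ED lab.** The flow chart schedules safety labs after the first dose at Visits 3, 4 and 5 (days 8, 15 and 29), at EoT/ED and at EoS, but not at Visit 6 (day 43). Using nominal days and no unscheduled samples:

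| Last dose (day) | Latest earlier lab (day) | Gap in days |
|---|---|---|
| 5 | none | – |
| 14 | 8 | 6 |
| 28 | 15 | 13 |
| 42 | 29 | 13 |
| 50 | 29 | 21 |
| 55 | 29 | 26 |

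In the first row the only earlier lab is the pre-dose baseline. SAP 7.8.2 requires at least one on-treatment value, so that participant leaves the analysis of each affected parameter.

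**4. Where the excluded lab goes.** In Table 6.7:2 the Week 10/EoS window opens at the stop date + X + 1. With a last dose on day 50 and an ED lab on day 55, the lab is 55 − 50 = 5 days after the last dose. The on-treatment phase ended on day 53, so the sample falls in the same window as the EoS visit two weeks later.

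**5. Is 3 days a pharmacokinetic choice?** Protocol 1.2.1 gives a terminal half-life of about 9 to 15 hours. Five half-lives are 5 × 9/24 = 1.9 to 5 × 15/24 = 3.1 days, so 3 days roughly matches plasma washout. The SAP does not offer this reason, and the protocol's 7-day period also covers pharmacodynamic effects.

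**The case against.** The strongest reply is that the windows are set endpoint by endpoint on purpose. Table 6.7:1 says so, the 7-day exception is stated openly, and a wide window for detecting abnormal values can sit beside a narrow one for the average effect on drug. The half-life makes 3 days plausible. All analyses are descriptive, the primary analysis is cancelled, and no decision depends on these displays. This stands as a limit on how much the point matters. It does not explain why eDISH, which also serves detection, takes the narrow window.

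Three stronger readings are tempting, and the documents do not support them.

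- *The ED labs drop out of the safety reporting.* They are reclassified, not deleted. They remain in the abnormality tables, the listings and the lab plots to EoS. The table combining aminotransferase and bilirubin elevations follows each elevation for 30 days and states no 3-day cut-off. Patients with elevated liver enzymes are listed, and hepatic events are adjudicated. An eDISH point moves only if the peak lies in the excluded sample; it disappears only if there is no other on-treatment value.
- *Most participants are affected.* The 57% is a share of permitted days. It becomes a share of participants only if ED visits are spread evenly, and no ED dates are given. If dosing stopped at or just before the ED visit, few are affected.
- *The 1-day vital-sign window is equally wrong* ("X= 3 days for safety laboratory; X=1 day for biomarkers and vital sign, respectively"). It excludes ED days 2 to 7. But peak concentration comes 0.5 to 1.0 hour after dosing, SAP 7.8.3 centres on pre-dose, 1-hour and 2-hour readings, and its figures include post-treatment visits. For a drug with this half-life the shorter window is defensible.

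**Conclusion.** The mismatch is real for labs. Followed as written, the SAP counts an ED lab from days 4 to 7 for abnormalities and excludes it from the last-value, minimum/maximum, reference-range and eDISH displays, although it lies within the protocol's own residual effect period. The last on-treatment value then comes from an earlier visit. For someone who stops between Visit 5 and Week 8 that is about day 29, up to 26 days before the last dose in the day-55 example. Complete loss is confined to participants who stop before Visit 3, have a late ED lab and have no other on-treatment sample.

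This rests on three assumptions: that ED visits took place as prescribed (the SAP records the decision to discontinue, not the visits), that the nominal schedule was kept, and that the on-treatment period named for eDISH is the lab phase of Table 6.1:1. The number of participants affected cannot be derived from the documents. The point is a cheap improvement to consistency, not evidence that a safety signal would be missed.

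**What to change.** In Tables 6.1:1, 6.7:1 and 6.7:2, set X for safety laboratory to 7 days, the rule already used for clinically significant values. Apply it to the last-value, minimum/maximum, reference-range and eDISH displays, and name the window for eDISH in SAP 7.8.2. Alternatively, keep X = 3, give the reason, and add a version of these displays based on the 7-day period. Either way, report how many ED labs fell on days 4 to 7, so that the reader can see the size of the effect.

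Replacing X costs one derivation parameter and a few words in the SAP; adding a version costs a second set of displays. The downside is that values taken several days after the last dose may dilute effects that reverse quickly, which favours showing both versions. ED labs later than day 7 stay post-treatment. The vital-sign window can remain at 1 day; a separately labelled ED row is optional.
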